11.1.3 Compliance with the Declaration of Helsinki

Refer to Declaration of Helsinki-Ethical Principles for Medical Research Involving Human Subjects.

11.1.4 Subject Confidentiality

All personal study subject data collected and processed for the purposes of this study should be maintained by the Investigator and his/her staff with adequate precautions as to ensure the confidentiality of the data in accordance with local, state, and federal laws and regulations.

Monitors, auditors, and other authorized representative of Sponsor, the IRB approving this study, FDA, the DHHS, other domestic government agencies, and other foreign regulatory agencies will be granted direct access to the study subject's original medical and study records for verification of the data and/or clinical trial procedures. Access to this information will be permitted to representatives of the aforementioned organizations to the extent permitted by law.

11.1.5 Documentation

Source documents may include a subject's medical records, hospital charts, clinic charts, the Investigator's study subject files as well as the results of diagnostic tests. The Investigator's copy of the eCRFs serves as the Investigator's record of a subject's study-related data. All data related to the study will be recorded on eCRFs to be provided by Sponsor via an EDC system. The Investigator is responsible for verifying that all data entries in the eCRFs are accurate and correct. The Investigator must sign the completed eCRFs before its submission to Sponsor.

The EDC system will be designed and used per 21 CFR Part 11 and the "Computerized Systems Used in Clinical Trials Guidance for Industry."

11.1.6 Retention of Documentation

All study related correspondence, subject records, consent forms, record of the distribution and use of the test article and copies of eCRFs should be maintained on file for the duration specified in each site's Clinical Trial Agreement and per the requirements of 21 CFR Part 312, "E6 Good Clinical Practice Guidance for Industry" part 5.5 and any local requirements.

11.2 Recording of Data on Source Document and Electronic Case Report Forms (eCRFs)

Adequate records will be maintained for the study including subject medical and surgical records, test reports, work sheets, nursing notes, signed informed consent forms, drug and device use records, adverse experience reports and information regarding subject discontinuation and reasons for discontinuation. All original source documentation will remain at the investigative site. Study data that are stored at the Investigator site in any electronic medical records system, that is not 21 CFR Part 11 compliant (e.g., Pentacam, OCT), should be printed and retained in the study files.

Sponsor personnel may require copies of source documents to be made available for off-site (remote) monitoring. Subject data should be de-identified prior to transmission to Sponsor's personnel not at the site.

All study data will be recorded onto eCRFs designed for the study.

11.3 Changes in the Conduct of the Study

Changes that affect the scientific soundness of the study or the rights, safety, or welfare of human subjects may also require FDA and IRB approval prior to implementation. The Sponsor and Investigator will obtain such approvals, if required.

Appendix A: ASSESSMENT INSTRUCTIONS

VISUAL ACUITY TESTING

Early Treatment Diabetic Retinopathy Study (ETDRS) Visual Acuity Chart: Modified Bailey-Lovie, Distance¹²

Illumination of the ETDRS Visual Acuity Charts and Room Illumination:

The standard ETDRS chart light box is used at the four- and one-meter test distances. The bulbs in the ETDRS chart light box are to be two 20 watt Daylight fluorescent tubes. Room illumination should be 50 to 100 foot-candles as measured with a photometer four meters and one meter from the ETDRS chart held four feet from the floor and directed toward the ceiling. ETDRS Charts will be changed as needed to maintain high contrast letters on a white background.

Uncorrected distance visual acuity (UCVA) must be assessed, followed by the determination of best spectacle-corrected distance visual acuity (BCVA).

Uncorrected Visual Acuity (UCVA):

Distance UCVA must be performed using calibrated Original Series ETDRS eye charts. Chart R will be used for UCVA testing. The total number of letters read correctly will be recorded.

Each of the two eyes is tested separately. The 4M ETDRS chart is presented and the subject is asked to proceed with reading the letters at the top of the chart. The subject should continue to read as many letters as possible in each subsequent row on the chart until he/she can no longer identify at least one letter correctly on a given line. At this point, the subject is asked to stop reading letters. The examiner tallies how many total letters the subject has correctly identified during the testing process and records this number. If the subject has correctly identified 20 or more total letters, visual acuity testing for the eye is complete.

If the subject has identified fewer than 20 letters correctly, place a +0.75 D spherical lens in front of the eye being tested and move the chart to a test distance of 1.0 meters. Once again, ask the subject to read the letters from the top of the chart. The subject should continue to read as many letters as possible in each subsequent row on the chart until he/she can no longer identify at least one letter correctly on a given line. At this point, the subject is asked to stop reading letters. The examiner tallies how many total letters the subject has correctly identified while looking through the +0.75 D spherical lens and records this number. UCVA testing for the eye is now complete.

Best-Spectacle Corrected Visual Acuity (BSCVA)

Distance BSCVA must be performed using calibrated Original Series ETDRS eye charts. Chart 1 is used for BSCVA testing of the right eye and Chart 2 is used for the left eye. The total number of letters read correctly will be recorded in the eCRF.

The distance from the subject's eyes to the ETDRS Visual Acuity Chart should be four meters. With the lens correction obtained by subjective refraction in the trial frame, the subject is asked to read

ETDRS Visual Acuity Chart 1 from the top with the right eye. It is emphasized to the subject that each answer will be scored so that adequate time should be allowed for each letter in order to achieve the best identification.

When the subject cannot read a letter, he/she is encouraged to guess if necessary. If the subject states that a letter is one of two letters, he/she is asked to choose only one letter. Only one reading is allowed for each letter. When a subject attempts to read the chart and comes to a line at which he/she cannot even guess, the examiner may stop the test.

If the number of letters read correctly at four meters is less than twenty, the test is repeated at one meter and both the four- and one-meter totals are recorded. Both eyes must be tested at four meters before the subject is moved up to the one-meter test distance. Prior to actual testing at one-meter, +0.75 spheres should be added to the correction already in the trial frame to compensate for the new distance. The subject may stand or sit for the visual acuity test at four meters, but must sit for the one-meter distance.

The same procedure for obtaining visual acuity for the right eye is used for the left eye, except that ETDRS Visual Acuity Chart 2 is used.

MANIFEST REFRACTION

Manifest refractions will be recorded on the source documents in the Investigator's usual notation (plus or minus cylinder format). All manifest refractions will be recorded on the CRFs for the study using minus cylinder format. Once the manifest refraction has been performed on both eyes, the BCVA should be performed. The ETDRS Refraction Chart R or any other visual acuity chart except Original Series ETDRS Visual Acuity Chart 1 or 2 may be used to determine the best distance lens correction, for each eye.

SLIT LAMP EXAMS

The slit lamp exam conducted by the Investigator should include a complete survey of the anterior segment including orbit/lids, lashes, pupil, conjunctiva, cornea, anterior chamber, iris, and lens. A grading of normal or abnormal will be noted at each visit. The following areas of the cornea should be examined – Epithelium, Descemet's membrane/endothelium, cornea-other. The grading of any abnormalities in any of the above mentioned areas should be recorded using the following scale:

0+ = 
1+ = 
2+ = 
3+ = 
4+ = 

In addition, the corneal clarity should be examined in detail with specific recordings and grading of any abnormalities using the following scale:

- 0+ = [REDACTED]
- 1+ = [REDACTED]
- 2+ = [REDACTED]
- 3+ = [REDACTED]
- 4+ = [REDACTED]

[REDACTED]

PENTACAM TOPOGRAPHY

[REDACTED] The median K_{max} value is to be reported in the eCRF. [REDACTED]

[REDACTED]

[REDACTED]

[REDACTED]

- [REDACTED]
- [REDACTED]
- [REDACTED]
 - [REDACTED]
 - [REDACTED]
 - [REDACTED]
 - [REDACTED]
 - [REDACTED]
 - [REDACTED]

SPECULAR MICROSCOPY

The methods used for the collection and analysis of specular microscopy data are critically important to minimizing the variability associated with these measurements. Common sources of variability in specular microscopy are:

- difficulty in returning to same location on the cornea at each visit;
- poor image quality (less than 100 countable cells);
- technician error

An acceptable image has:

- distinct cells;
- at least 100 identifiable (countable) cells as a minimum, 150 cells preferred; and
- cells that can be grouped in a uniform area.

To capture a good image:

- make sure the subject is comfortable;
- instruct the subject to blink;
- instruct subject not to move and to open eyes wide;
- instruct subject to focus straight ahead or on the green light;
- be patient; and
- if necessary, use the manual setting. (Note that the use of the manual setting may require additional training).

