
Safety Evaluations:
	
 • Pentacam Pachymetry • Intraocular pressure (IOP) • Adverse events (AEs) • Best Spectacle Corrected Visual Acuity (BSCVA) assessed using the Early Treatment of Diabetic Retinopathy Study (ETDRS) charts • Slit lamp biomicroscopy • Manifest refraction • Dilated fundus exam • Endothelial Cell Count (ECC) • Macular Optical Coherence Tomography (OCT) [at select sites, in at least 80 eyes in the CXL treatment group and at least 40 eyes in the Sham treatment group]

Efficacy Evaluations:
	
 • [REDACTED] ■ [REDACTED] ■ [REDACTED] ■ [REDACTED]

Sample Size/Power:
	
The sample size for this study is based on unequal group sizes with the number of eyes in the crosslinked group being 2 times greater than in the control group (2:1 randomization). Two hundred forty (240) eyes (160 in the cross-linking treatment

	
group and 80 in the control group) provides approximately 80% power [REDACTED]
 
[REDACTED] This
 
[REDACTED] The sample size for this study is determined
 
to be 275 eyes [REDACTED]

--	--

STUDY SCHEDULE

Procedure	Screen	Treatment	POST-TREATMENT VISITS ¹³						
			1 DAY	3 Day	1 WK	1 MO	3 MO	6 MO	12 MO
	Visit 1	Visit 2	Visit 3	Visit 4	Visit 5	Visit 6	Visit 7	Visit 8	Visit 9/ Exit Visit
	Day -45 to -1	Day 0	Day 1 to 2	Day 3 to 4	Day 5 to 14	Day 21 to 42	Day 84 to 98	Day 180 to 210	Day 360 to 390
Informed Consent/Assent	X								
Medical & Medication History ¹	X	X	X	X	X	X	X	X	X
Demographics	X								
BSCVA ²	X					M ¹¹	M ¹¹	M ¹¹	M ¹¹
UCVA ²	X		X	X	X	M ¹¹	M ¹¹	M ¹¹	M ¹¹
Manifest Refraction	X					M ¹¹	M ¹¹	M ¹¹	M ¹¹
Intraocular Pressure Measurement ³	X					X	X	X	X
Slit Lamp Exam	X	X ⁹	X	X	X	X	X	X	X
Dilated Fundus Examination ⁴	X						X	X	X
Pentacam Tomography and Pachymetry ⁵	X					X	X	X	X
Ultrasound Pachymetry		X ¹⁰							
Endothelial Cell Count ⁶	X						X	X	X
Macular and anterior segment OCT ⁷	X					X ¹²	X	X	X
NEI-VFQ 25	X					X	X	X	X
Adverse Event Query		X	X	X	X	X	X	X	X
Study Treatment		X							
Pregnancy Test ⁸		X							

¹Ocular status and/or history including history of contact lens wear. Non-specific questioning should be used at each visit to determine other vision-related complaints, complications, or adverse events.

²Distance BSCVA and UCVA will be performed using a calibrated ETDRS eye chart and recording the total number of letters that are read correctly.

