5.2 Safety Evaluations

The following safety parameters will be assessed:

- Incidence of treatment emergent ocular AEs reported during the study
- Percentage of eyes with loss in BSCVA of 3 lines or more from pre-treatment baseline

[REDACTED]

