2.2.4.3 Visual Acuity (BSCVA and UCVA)

The number of letters read from the Early Treatment of Diabetic Retinopathy Study (ETDRS) chart from the BSCVA and UCVA will be evaluated at screening, baseline, and each follow-up exam beginning at 1 month.

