3.8.3 BSCVA and UCVA

For the safety analysis, BSCVA and UCVA will be presented in terms of the number of ETDRS letters lost/gained or not changed from baseline by each treatment group.

- [REDACTED]
- [REDACTED]
- [REDACTED]
- [REDACTED]
- [REDACTED]
- [REDACTED]
- [REDACTED]
- [REDACTED]
- [REDACTED]

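### Does the lack of a visible rule for joining the 4 m and 1 m letter counts put the BSCVA loss endpoint at risk?

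*Protocol*

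**What the plan says.** For BSCVA, Protocol Appendix A states the general rule first: "The total number of letters read correctly will be recorded in the eCRF". It then deals with eyes that read fewer than 20 letters at 4 m: "the test is repeated at one meter and both the four- and one-meter totals are recorded".

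For uncorrected acuity (UCVA), the examiner counts the letters "correctly identified during the testing process and records this number". If that count is below 20, the chart is moved to 1 m and a second count follows: "The examiner tallies how many total letters the subject has correctly identified while looking through the +0.75 D spherical lens and records this number".

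Elsewhere the value is singular. Footnote 2 of the Study Schedule speaks of "recording the total number of letters that are read correctly". SAP 2.2.4.3 says: "The number of letters read from the Early Treatment of Diabetic Retinopathy Study (ETDRS) chart from the BSCVA and UCVA will be evaluated". SAP 3.8.3 says: "BSCVA and UCVA will be presented in terms of the number of ETDRS letters lost/gained or not changed from baseline".

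Protocol 5.2 lists as a safety evaluation: "Percentage of eyes with loss in BSCVA of 3 lines or more from pre-treatment baseline". Protocol 10.8 and SAP 3.4.4 make loss in BSCVA a primary safety endpoint.

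**The concern.** A letter at 1 m is larger to the eye than the same letter at 4 m, so counts from the two distances are not on one scale. An eye that reads 20 letters at 4 m is scored from that distance alone, while an eye that reads 19 also has a 1 m count. If the single score is built by using the raw 1 m count, or by adding the two counts, an eye that gets worse and falls below 20 letters can appear to improve. If only the 4 m count is used, eyes that start very low run into the floor at zero.

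The endpoint at stake counts eyes with a 3-line loss, in a trial asking whether a new procedure is safe. Such losses are counted eye by eye, so a few misclassified eyes could alter the figure. Up to 20 sites enter data, and the test instructions in Appendix A and the variable description in SAP 2.2.4.3 carry no redaction that could hide a joining rule.

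**Working it through.** The plan gives no figure on this point to reproduce. The check is whether the literal readings really go wrong, and then whether the plan leaves an analyst unable to avoid them.

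**Inputs from the documents:** test distances of 4 m and 1 m, and the 20-letter threshold (Protocol Appendix A); loss of 3 lines or more (Protocol 5.2); change taken as follow-up minus baseline (SAP 3.1.3).

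**Assumptions, not in the documents:** 5 letters and 0.1 log unit per line, and 70 letters per chart. Then 3 lines = 15 letters, and moving from 4 m to 1 m is worth log10(4)/0.1 = 6.02 lines, or 6.02 × 5 = 30.1, about 30 letters.

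**A true 15-letter loss.** Let L be the baseline count at 4 m.

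| Reading | Baseline | Baseline score | Follow-up score | Scored change |
|---|---|---|---|---|
| 1 m count replaces 4 m count below 20 | L = 20 to 34 | L | (L − 15) + 30 | +15 |
| 4 m and 1 m counts added below 20 | L = 20 to 34 | L | (L − 15) + (L − 15 + 30) = 2L | +L, so +20 to +34 |
| 4 m count only | L = 1 to 14 | L | 0 (floor) | −L, so −1 to −14 |
| Common scale: 4 m count + 30 if 20 or more, otherwise 1 m count | L = 20 to 34 | L + 30 | (L − 15) + 30 | −15 |

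**True gains of g = 1 to 15 letters that cross 20.** There are 1 + 2 + … + 15 = 120 combinations. With replacement the scored change is g − 30, that is −29 to −15. With addition it is g − L − 30, from −20 (L = 5, g = 15) to −48 (L = 19, g = 1). All 120 would be flagged as losses of 15 letters or more.

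**All score pairs.** Let the true score, expressed at 4 m, run over the integers −30 to 70 (101 values). Pairs with a loss of 15 or more number 86 + 85 + … + 1 = 86 × 87/2 = 3741. Addition misses 1033, replacement misses 885, 4 m only misses 465, and the common scale misses none. These count possible pairs; they are not event rates.

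**Sensitivity to the assumed shift.** With 20, 25 or 35 letters instead of 30, replacement scores a true 15-letter loss as −15 + 20 = +5, −15 + 25 = +10 or −15 + 35 = +20. The direction of the fault does not depend on the exact constant.

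**Can an analyst avoid the fault?** Three points settle this.

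1. *The data exist.* The BSCVA text keeps both totals, and the UCVA text records a number at each distance. Every reading in the table, including the common scale, can be computed from them.
2. *The fault is conspicuous.* Under replacement, a fall from 20 to 19 letters scores (19 + 30) − 20 = +29. SAP 3.1.2 puts all clinical data into listings, where such jumps would occur exactly at the threshold.
3. *The usual remedies agree.* Below 20 letters, one may take the 1 m count, or the 4 m count plus the 1 m count capped at 30. With a 30-letter shift and L from 0 to 19, the first is L + 30 and the second is L + min(30, L + 30) = L + 30.

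**Would writing in a constant be safe?** Not from these documents. With + 30 fixed and a true shift of 35, a 15-letter loss from 20 to 34 scores (L − 15 + 35) − (L + 30) = −10 and is missed. With a true shift of 20, a 5-letter loss that crosses the threshold scores (L − 5 + 20) − (L + 30) = −15 and is flagged.

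**Where would a rule sit?** Text is redacted after the 3-line criterion in Protocol 5.2, after the BSCVA endpoint in Protocol 10.8 and SAP 3.4.4, after the change-from-baseline definition in SAP 3.1.3, at the start of SAP 3.8, and in all nine bullets under SAP 3.8.3.

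**The case for a change.** The strongest case for a change is that the two unredacted places a site or programmer would consult first, Appendix A and SAP 2.2.4.3, give no rule, and that an unwritten convention is not a specification when many sites feed a primary safety endpoint. Every unconverted reading misses some real 3-line losses at every shift tried. Fixing the rule before database lock would also stop anyone choosing it after seeing the data, and it would cost one derivation.

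Part of this stands. The readable text does not join the two counts, and the arithmetic is right under its assumptions.

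The rest is weaker. The sentence about a single eCRF total and the sentence about two totals read naturally as a general rule and its exception below 20 letters, so nothing shows that sites must build the score themselves. The eCRF is not among the documents, so a missing second field is conjecture. Redacted analysis text cannot be counted as missing. Harm also needs eyes that cross 20 letters, or eyes that start at 1 to 14 letters under the 4 m reading. The ocular inclusion criteria are redacted, so a baseline acuity limit cannot be ruled out. Nor is the direction of any error known: the same readings that hide true losses also turn true gains into apparent losses.

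**Conclusion.** No change to the plan is needed. This is missing scoring detail of a kind that an analyst supplies as a matter of course: both counts are taken, and putting two test distances on one scale is the only sensible way to form a change in letters. The rule may also already be in redacted text or in the eCRF.

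The possible error for a single affected eye is large: +15 to +34 letters scored for a true 15-letter loss, given a 30-letter shift. It arises only if someone uses raw counts, and only in eyes near or below 20 letters at 4 m. Their number cannot be estimated from the documents and may be small. The Kmax primary and secondary endpoints do not use these scores.

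The conclusion rests on both counts being retained for eyes tested at 1 m, as Appendix A says for BSCVA and implies for UCVA. It would need another look if the unredacted SAP held no rule and the eCRF kept only one undefined number.

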APPENDIX B: 

**PROT-00009 Rev B
ACP-KXL-308 PROTOCOL**

CONFIDENTIAL
Effective: 11 OCT 2018
Page 60 of 69

Sponsor: Avedro, Inc.

Subject Number _____

Subject Initials _____

Protocol: ACP-KXL-308

Date (mm/dd/yyyy) _____

___/___/20__

SCREEN

1 MONTH

3 MONTH

6 MONTH

12 MONTH

VISIT:

This questionnaire has been modified to remove the appendix of optional additional questions (A1-A13) that appeared on the original questionnaire and to add a clinical study specific header to each page of the questionnaire.

The following is a survey with statements about problems which involve your vision or feelings that you have about your vision condition. After each question please choose the response that best describes your situation.

Please answer all the questions as if you were wearing your glasses or contact lenses (if any).

Please take as much time as you need to answer each question. All your answers are confidential. In order for this survey to improve our knowledge about vision problems and how they affect your quality of life, your answers must be as accurate as possible. Remember, if you wear glasses or contact lenses, please answer all of the following questions as though you were wearing them.

[figure not shown]
INSTRUCTIONS:

- 1 In general we would like to have people try to complete these forms on their own. If you find that you need assistance, please feel free to ask the project staff and they will assist you.
- 2 Please answer every question (unless you are asked to skip questions because they don't apply to you).
- 3 Answer the questions by circling the appropriate number.
- 4 If you are unsure of how to answer a question, please give the best answer you can and make a comment in the left margin.
- 5 Please complete the questionnaire before leaving the center and give it to a member of the project staff. Do not take it home.
- 6 If you have any questions, please feel free to ask a member of the project staff, and they will be glad to help you.

STATEMENT OF CONFIDENTIALITY:

All information that would permit identification of any person who completed this questionnaire will be regarded as strictly confidential. Such information will be used only for the purposes of this study and will not be disclosed or released for any other purposes without prior consent, except as required by law.

Version date: 28-Nov-2017

Page 1 of 69

Sponsor: Avedro, Inc.

Subject Number _____

Subject Initials _____

Protocol: ACP-KXL-308

Date (mm/dd/yyyy)

___/___/20__

SCREEN

1 MONTH

3 MONTH

6 MONTH

12 MONTH

VISIT:

Visual Functioning Questionnaire - 25

[REDACTED]

[REDACTED]

[REDACTED]

[REDACTED]

|

[REDACTED]

[REDACTED]

[REDACTED]

[REDACTED]

|

[REDACTED]

[REDACTED]

[REDACTED]

|

[REDACTED]

Sponsor: Avedro, Inc.
Protocol: ACP-KXL-308

Subject Number _____ Subject Initials _____
Date (mm/dd/yyyy) ___/___/20__

SCREEN 1 MONTH 3 MONTH 6 MONTH 12 MONTH

VISIT:

[REDACTED]

[REDACTED]

[REDACTED]

[REDACTED]

[REDACTED]

Sponsor: Avedro, Inc.
Protocol: ACP-KXL-308

Subject Number _____ Subject Initials ____
Date (mm/dd/yyyy) ___/___/2_0__

SCREEN 1 MONTH 3 MONTH 6 MONTH 12 MONTH

VISIT:

[REDACTED]

[REDACTED]

[REDACTED]

[REDACTED]

[REDACTED]

6

PROT-00009 Rev B
ACP-KXL-308 PROTOCOL

CONFIDENTIAL
Effective: 11 OCT 2018
Page 64 of 69

Sponsor: Avedro, Inc.
Protocol: ACP-KXL-308

Subject Number _____ Subject Initials _____
Date (mm/dd/yyyy) ___/___/2_0___

	SCREEN	1 MONTH	3 MONTH	6 MONTH	12 MONTH
VISIT:					

[REDACTED]

[REDACTED]

[REDACTED]

[REDACTED]

[REDACTED]

[REDACTED]

[REDACTED]

No [REDACTED]

(Circle One)
[REDACTED]

[REDACTED]

[REDACTED]

[REDACTED]

[REDACTED] date: 28-Nov-2017

[REDACTED]

Sponsor: Avedro, Inc.
Protocol: ACP-KXL-308

Subject Number _____ Subject Initials ____
Date (mm/dd/yyyy) ___/___/2_0___

VISIT: SCREEN 1 MONTH 3 MONTH 6 MONTH 12 MONTH

[REDACTED]

15. [REDACTED]

[REDACTED]

[REDACTED]

Sponsor: Avedro, Inc.
Protocol: ACP-KXL-308

Subject Number _____ Subject Initials _____
Date (mm/dd/yyyy) ___/___/20__

	SCREEN	1 MONTH	3 MONTH	6 MONTH	12 MONTH
VISIT:					

[REDACTED]

[REDACTED]

[REDACTED]

[REDACTED]

[REDACTED]

[REDACTED]

[REDACTED]

[REDACTED]

[REDACTED]

[REDACTED]

[REDACTED]

[REDACTED]

Sponsor: Avedro, Inc.
Protocol: ACP-KXL-308

Subject Number _____ Subject Initials _____
Date (mm/dd/yyyy) ___/___/20__

	SCREEN	1 MONTH	3 MONTH	6 MONTH	12 MONTH
VISIT:					

[REDACTED]

(Circle One On Each Line)

	SCREEN	1 MONTH	3 MONTH	6 MONTH	12 MONTH
[REDACTED]					
